### **8. Subject Safety Monitoring:**

#### *a. Parameters to be monitored*

#### **General Subject Monitoring**

Over the course of the outpatient visits to the NIH, Clinical Center, the Principal Investigator, Associate Investigators, Independent Study Monitor, Research Nurse Coordinator, and attending clinical staff will monitor the participants for distress, discomfort, and desire to discontinue the study. Participants will be provided with the contact information of the Principal Investigator should concerns arise in between visits.

#### **Alprazolam Subject Monitoring**

For the alprazolam experiment, a certified healthcare provider (nurse, nurse practitioner, or physician) will be on hand throughout the procedure and will be responsible for participants' discharge. A sedation assessment, the Observer's Assessment of Alertness/Sedation Scale (Chernik 1990), will be administered by the certified healthcare provider prior to and following the procedure before discharge. The certified healthcare provider will also contact the participant the following day after each testing session to ensure that there are no adverse reactions to the drug or experimental procedures. This study has been completed.

### **Increased symptom severity**

If, during the course of assessing a participant, a study staff member identifies a significant worsening of symptoms, a mental health provider currently treating the participant will be contacted, and the necessary treatment steps (e.g., hospitalization, referral to a care provider, etc.) will be offered.

**Risk for self-harm:** Participants will be monitored for risk for self-harm via a history and physical exam and clinical interview on Visit 1, and subsequently during all study visits. If a participant is considered a positive screen for self-harm, the participant will not be able to leave the premises until evaluated for safety and study procedures will be terminated for that day. If following the safety/mental health evaluation it is determined that a participant is at risk for self-harm, the participant will be excluded from the study. Participant transfers to alternative medical facilities will be conducted according to NIH, Clinical Center Guidelines. For off-hour psychiatric emergencies, the study investigator's voice message instructs participants to call 911 or visit the nearest Emergency Department. If a participant leaves a voicemail in distress, the clinical team will attempt to make contact with the participant within one business day. If contact by phone is successful, the participant will be triaged by phone and offered a list of mental health resources. If the participant does not respond to calls, the clinical team will try calling an alternative number if available.

*b. Toxicity tables/ criteria to be used*

N/A

*c. Criteria for individual subject withdrawal*

Participants will be withdrawn from the study if the Principal Investigator determines a serious adverse event is related to the study procedures or if the severity of an adverse event warrants withdrawal. Participants will also be withdrawn if they develop high levels of anxiety, fear, or panic during/from any shock experiments. Participants will also be excluded from the study, if they become at risk for self-harm. Additional criteria include withdrawal of consent and/or participant decision, non-compliance with protocol procedures, and lab results that preclude participation (i.e., positive drug and/or pregnancy result). This study nor the NIH will pay for outside treatment.

## **9. Outcome Measures:**

*a. Primary*

Functional magnetic resonance imaging (fMRI), measuring the event-related haemodynamic response related to neural activity in the brain.

Magnetoencephalography (MEG) a neuroimaging technique employed in the current protocol to measure the event-related magnetic fields produced by

electrical activity in the brain via extremely sensitive devices such as superconducting quantum interference devices (SQUIDS).

b. Secondary

Psychophysiological measures of anxious arousal including the skin conductance response (SCR), heart rate, respiration, and EMG measures of the fear-potentiation of the startle reflex.

Salivary cortisol assays to measure the stress response to the cold pressor, saliva will be collected at several intervals throughout the session with plain cotton swab Salivettes. All samples will be frozen and stored at -70°C until assayed in one of the freezers located in bldg 10, 2D corridor. On the day of assay, the Salivette tubes will be thawed at room temperature and centrifuged at 3000g for 10 minutes. Cortisol concentration in saliva will be measured by enzyme immunoassay (Salimetrics LLC, State College, PA). Management and analysis of saliva samples will be done by [name], in the Section on Genetic Developmental Epidemiology. Samples will be number coded, stored for approximately a year, and then properly disposed in medical waste.

Self-reported measures of anxiety, level of risk, and CS-US contingency awareness.

## 10. Statistical Analysis:

### a. Analysis of data/ study outcomes

Analysis of functional imaging data involves a series of initial steps including realignment (i.e., correction for subtle head movement). Hypotheses regarding task-associated changes in the BOLD signal will initially be tested by analyzing task-related hemodynamic responses in four regions-of-interest (ROI) selected based on hypothesized areas of activation: the amygdala, the dorsal anterior hippocampus (Williams et al., 2001), the anterior insula, and the anterior cingulate. These ROI will be defined using AFNI (Analysis of Functional NeuroImages; <http://afni.nimh.nih.gov/afni/>). The ROIs will be defined on each subjects' anatomical MRI image, and the corresponding changes in BOLD data will be extracted from fMRI images that have been coregistered to the anatomical MRI. Correction to control for inflation of  $\alpha$  (Type I error) will be applied to the tests performed on these 8 regions (4 regions in each hemisphere).

In addition, a voxel-wise analysis will be performed to investigate activations outside of these regions using SPM 8 (Statistical Parametric Mapping; <http://www.fil.ion.ucl.ac.uk/spm/>). Spatial transformation and smoothing will be performed prior to the voxel-wise analysis. This analysis will assess activations in areas outside the ROIs defined *a priori*, as well as to localize the voxel-coordinates for the peak difference between conditions within the primary ROIs. We will model the effects of presenting the cues depending on the background, and of presenting the background itself on BOLD activity.

The factor context (neutral, predictable, unpredictable) will be entered as a blocked factor to model the background state during these 2-min conditions. In addition, the transient response to the cues will be modeled with respect to the onset of the cue. The hypothesis is that in the areas critical for cue fear there will be a transient response to the cue in the predictable relative to the neutral and unpredictable condition. This model of analysis constitutes a mixed block/event-related design.

All experiments except for those that include patient groups will use within-subject designs, such that each participant will experience each comparison condition of interest (note: this does not imply that ALL subjects will participate in ALL procedures, just that the procedures in which they elect to participate will include the conditions necessary to perform the intended analyses). Experiments that include patients will operate both within-subject and between-subject designs; the within-subject factors being the experimental conditions, and the between-subject factor being subject group (patient or healthy control).

*b. Criteria for significance*

For voxel-wise analyses on normalized whole brain data, we will control false positive rates per map at  $\alpha=.05$ , using random-effects models (see e.g., Zarahn, 2000; Zarahn et al., 2000; Pine et al., 2001; 2002).

*c. Power analysis*

Sample size of 15 subjects with good quality data (no major artifacts or other problems) is usual for previous published studies on activation of limbic structures, such as Phelps et al. (1999; N=12), and Whalen et al. (1998; N=10). Although power computations are possible for ROI analyses using conventional statistical tests in which average BOLD signal intensities are treated as dependent variables, because the current study constitutes a pilot experiment that has not been previously performed, the mean and standard deviation of the changes in BOLD responses that will be obtained using the proposed methods are not known. In general, with sample sizes as small as  $n=10$  and for alpha = .05 (two-tailed), power exceeds .80 to detect effect sizes of 1.2 in one pre-specified brain region. Fortunately, most fMRI studies of neurobiologically meaningful task-associated changes in BOLD signal document larger effects than this. For patient subtypes, (i.e., GAD, SAD, panic, phobia, PTSD, and MDD) an  $N$  of 30 will be targeted for each study. This larger sample size will provide us with a greater range of symptom severity in order to conduct correlation analyses with regional brain activity and it will buffer against potentially higher rates of attrition (excessive motion, symptom-related dropout) in our psychiatric samples.

For the Time Perception, cognitive task, a power analysis was conducted to determine the number of participants that will be used for that sub-study. In a previous fMRI experiment, our largest effect size ( $\eta^2=0.24$ ) was for brain activation in the insula under our anxiety manipulation. Assuming a somewhat smaller effect size ( $\eta^2=0.20$ ) due to regression to the mean, if we set power at .90 and experiment-wise, two-tailed alpha at 0.05. Based on these parameters, we will need 46 subjects per experiment. Assuming 4

subjects to initially adjust the experimental procedure, a N of 50 subjects will be the target for the experiment.

For the first modified version of the *Motivation/ "Monetary Incentive Delay" Task*, we propose to collect 80 participants on the 3T fMRI scanner in order to assess the role of between subject factors such as gender and trait anxiety on neural responses to incentives. Assuming a medium effect size ( $R^2=0.15$ ), a power of 0.8, and an alpha of 0.05, power analyses suggest that we would require a sample of 75 participants to detect an association employing two-tailed multiple regression analyses. Assuming that five participants are lost due to head motion, we will need to collect 80 participants to detect a medium sized effect of gender or trait anxiety on these neural responses.

For the first modified version of the *Motivation/ "Monetary Incentive Delay" Task*, we propose to collect 30 participants on the 7T fMRI scanner in order to assess the role of small midbrain structures in reward/threat processing. Assuming a slightly larger effect size due to the improved signal to noise ratio of 7T imaging (Cohen's  $d_z=0.6$ ), a power of 0.8, and an alpha of 0.05, power analyses suggest that we would require a sample of 24 participants to detect a difference between conditions employing two-tailed paired T tests. Assuming five participants are lost due to head motion. we will need to collect 30 participants to detect a medium sized effect of trial type on neural responses to incentives.

For the second modified version of the *Motivation/ "Monetary Incentive Delay" Task*, we propose to collect 40 participants on the MEG scanner to assess anticipatory responses to aversive and monetary motivational stimuli. Assuming a medium effect size (Cohen's  $d_z=0.5$ ), a power of 0.8, and an alpha of 0.05, power analyses suggest that we would require a sample of 34 participants to detect a difference between conditions employing two-tailed paired T tests. Assuming five participants are lost due to head motion, we will need to collect 40 participants to detect a medium sized effect of trial type on anticipatory neural responses.

Collectively, the three research projects listed above ( $80+30+40=150$ ) will increase our accrual from 30 to 150 participants for the *Motivation/ "Monetary Incentive Delay" Task*.

For the first modified version of the *Active Avoidance of Signaled Threat Paradigm*, we propose to collect 45 healthy participants without war-zone exposure on the fMRI scanner. Assuming a medium effect size (Cohen's  $d_z=0.5$ ), a power of 0.8, and an alpha of 0.05, power analyses suggest that we would require a sample of 34 participants to detect a difference between conditions employing two-tailed paired T tests. Assuming ten participants are lost due to head motion and poor performance, we will need to collect 45 participants to detect a medium sized effect of trial type on neural responses during avoidance.

For the second modified version of the *Active Avoidance of Signaled Threat Paradigm*, we propose to collect 45 healthy participants without war-zone exposure on the MEG scanner. Assuming a medium effect size (Cohen's  $d_z=0.5$ ), a power of 0.8, and an alpha

of 0.05, power analyses suggest that we would require a sample of 34 participants to detect a difference between conditions employing two-tailed paired T tests. Assuming ten participants are lost due to head motion and poor performance, we will need to collect 45 participants to detect a medium sized effect of trial type on neural responses during avoidance.

Collectively, the two research projects listed above (45+45=90) will increase our accrual from 30 to 90 healthy participants without war-zone exposure for the *Active Avoidance of Signaled Threat Paradigm*.

*d. Accrual number*

Our ceiling is set at 1952 participants. This will account for the addition of patients (726) as well as a separate group of 1226 healthy matched (age, sex, IQ) controls.

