C) A third hypothesis is that while anticipation of unpredictable shocks will reduce GABA concentration, leading to low peak frequency of stimulus-induced gamma oscillations in the occipital cortex and increases BOLD response, the benzodiazepine alprazolam will have the opposite effect (increased GABA, leading to high peak gamma frequency and decreased BOLD signal).

D) A fourth hypothesis is that under threat of shock, prefrontal executive control regions will be less successfully engaged by patients with high anxiety or MDD than healthy controls. Further, we predict that both patient groups will recruit the cortical and subcortical limbic regions (e.g., amygdala, bed nucleus of stria terminalis (BNST), and insula) to a greater extent than healthy controls when under threat of shock. In contrast to anxiety patients, MDD patients will additionally recruit subgenual/rostral ACC in response to threat.

E) In the PTSD hippocampus investigation, we hypothesize that the hippocampus and dorsolateral prefrontal cortex (dlPFC) will play a key role in the effect of anxiety on BPS Task performance and that participants with PTSD will exhibit amplified pattern separation deficits. We also hypothesize that pattern separation deficits will be associated with PTSD symptom severity in the dentate gyrus as indicated in the high-field 7-Tesla resting state scan. Lastly, we hypothesize that the PTSD group (vs. no-PTSD) will have increased hippocampal-dependent spatial memory deficits on the Morris water maze (MWM) task.

F). We hypothesize that during the AAST paradigm, participants will exhibit enhanced neural responses to the avoidance cue during the threat-of-shock condition, within areas of the medial prefrontal cortex, amygdala, and striatum. Furthermore, we hypothesize that participants with PTSD will exhibit reduced medial prefrontal cortex responses during threat contexts, and elevated avoidance behavior. Lastly, we hypothesize that individual differences in avoidance behavior will be associated with the magnitude of task elicited neural activity within the medial prefrontal cortex, amygdala, and striatum.

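### Active Avoidance fMRI: the stated power of .80 is for one test at undivided alpha .05, but Section 10 corrects over regions; under Bonferroni, power for a given region is about .52 (8 tests)

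*Combined protocol and SAP*

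**What the plan says.** Section 10.c, in the paragraph on the first modified version of the Active Avoidance of Signaled Threat task, sets the sample: "we propose to collect 45 healthy participants without war-zone exposure on the fMRI scanner". The inputs are Cohen's dz 0.5 and two-tailed paired t tests, with "a power of 0.8, and an alpha of 0.05, power analyses suggest that we would require a sample of 34 participants" (the Monetary Incentive Delay MEG paragraph uses the same words). The step to enrolment is "Assuming ten participants are lost due to head motion and poor performance, we will need to collect 45 participants". The paragraph names no brain region, no test family and no correction.

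Section 10.a gives the analysis: "Hypotheses regarding task-associated changes in the BOLD signal will initially be tested by analyzing task-related hemodynamic responses in four regions-of-interest (ROI"). The four are the amygdala, the dorsal anterior hippocampus, "the anterior insula, and the anterior cingulate. These ROI will be defined using AFNI". Correction for inflation of alpha is then promised: "Type I error) will be applied to the tests performed on these 8 regions (4 regions in each hemisphere"). The method is not named, and the rule is not limited to particular sub-studies. Areas outside the list go to an additional voxel-wise analysis, for which Section 10.b controls false positives per map at .05.

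For this task, hypothesis F in Section 2 predicts that "participants will exhibit enhanced neural responses to the avoidance cue during the threat-of-shock condition, within areas of the medial prefrontal cortex, amygdala, and striatum". The general power statement in 10.c is explicitly narrower than the Active Avoidance paragraph: "power exceeds .80 to detect effect sizes of 1.2 in one pre-specified brain region".

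**The concern.** The sample size rests on one test at the full .05. The analysis section describes several regional tests that share an error rate. A threshold stricter than .05 for each region lowers the chance of detecting a true effect in that region, so the .80 in 10.c and the analysis in 10.a do not describe the same thing.

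The regions also do not line up. Of the three areas in hypothesis F, the amygdala is on the 10.a list. Medial prefrontal cortex is partly covered by the anterior cingulate, which Section 1.3 itself links to medial PFC. The striatum is absent and would fall to the voxel-wise analysis. A reader therefore cannot tell which region, family or success rule the .80 refers to.

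At stake is the stated justification for enrolling 45 healthy volunteers, and the effect size the sub-study can claim to detect once the planned correction is applied.

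**Working it through.** **Inputs from the documents.** dz = 0.5, power .80, alpha .05, two-tailed paired t test, 34 evaluable, 45 enrolled, ten lost (10.c); 8 regional tests (10.a); three areas (hypothesis F). 45 − 10 = 35 evaluable.

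**Formula.** For n pairs, df = n − 1 and noncentrality δ = dz·√n. With c the two-sided critical t at level α, power = P(T > c) + P(T < −c), where T is noncentral t with df and δ.

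**Reproducing the plan's figure** (undivided α = .05):
- n = 33: δ = 0.5·√33 = 2.872, c = 2.037, power .795.
- n = 34: δ = 0.5·√34 = 2.915, c = 2.034, power .808.

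The smallest n reaching .80 is 34, so the plan's number is correct for one undivided test.

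**Applying a correction.** Bonferroni is an assumption, with α = .05/k: .0167 for k = 3 and .00625 for k = 8. The 8 comes from 10.a. The family of 3 is an assumption taken from hypothesis F.

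| Evaluable n | k = 1 | k = 3 | k = 8 |
|---|---|---|---|
| 34 | .81 | .65 | .51 |
| 35 | .82 | .67 | .52 |
| 45 (no losses) | .91 | .80 | .68 |

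Worked cell, n = 35 and k = 8: δ = 0.5·√35 = 2.958, c = 2.915, power .52. If the three areas were split by hemisphere (k = 6), power at n = 35 would be .57.

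**Effect detectable with 80% power at n = 35:** dz 0.57 over 3 tests and dz 0.64 over 8, against the assumed 0.5.

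**Less conservative methods** (simulation at n = 34; ranges cover how many regions are truly active and between-region correlations of 0 to .6, which are assumptions). Per-region power with Holm is .65 to .75 over 3 tests and .51 to .63 over 8. With false-discovery-rate control it is .65 to .78 over 3 and .51 to .78 over 8. All stay below .80.

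**Other success rules** (n = 34, Bonferroni over 3, same correlations):
- At least one region: .85 to .96 if all three are truly active, .79 to .88 if two are, .65 if one is.
- All three regions: .28 to .43.

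**Monetary Incentive Delay, 7T.** At dz 0.6 and undivided .05, n = 24 gives .804, so its 24 likewise assumes one undivided test.

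**The case against.** The strongest reply is that 10.c is not wrong as written. It powers one two-tailed contrast at .05, the 34 is right, and it does not promise .80 in every region after correction. That stands as to the arithmetic. It does not settle the matter, because the paragraph never says which single test it means, whereas the general statement in the same section limits itself to one region fixed in advance.

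Second, areas outside the four listed regions are not without a plan: the voxel-wise analysis covers them, with its own error control. That is correct, and it applies to the striatum and to the 7T midbrain target. But control per map is also a correction, so it does not restore an undivided .05. The regional figures above do not estimate voxel-wise power, which could be better or worse.

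Third, the 8-test family is tied to wording that goes on to model neutral, predictable and unpredictable contexts, while Active Avoidance uses safe and threat blocks. Hypothesis F also does not name the hippocampus or the insula. The .51 to .52 therefore rests on reading an unqualified rule as general. The family of three is not described anywhere in the plan.

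A reader might go further and infer that .80 fails under any success rule. The documents do not support that: at-least-one power can exceed .80 when several regions are truly active, and per-region power over three tests is .80 if no one is lost. Nor do they support calling 34 an arithmetic error.

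**Conclusion.** The point holds as a mismatch between the sample-size alpha and the planned error control. The stated .80 is not the power for a given region under the correction in Section 10. For a listed region that hypothesis F also names, such as the amygdala, it is .52 at 35 evaluable if the correction is Bonferroni over the 8 tests, or .67 over three.

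These figures rest on dz 0.5 as assumed in 10.c, on Bonferroni, and on the family size. The plan leaves the correction method and the success rule unstated, and does not say which regions form the family for this task. It would go too far to conclude that the sub-study is underpowered or needs more participants: with one named primary region, the existing 45 are enough on the plan's own assumptions. The repair should be made, but it does not call the sub-study's validity into question.

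**What to change.** For Active Avoidance fMRI, adopt one of two wordings.

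1. Name one primary region, stating how left and right are handled (10.a counts them separately), and one contrast tested at two-tailed .05. Make all other regions secondary and corrected. The stated .80 is then true (.82 at 35 evaluable).
2. Keep a multi-region family. State the family (reconciled with hypothesis F), the correction method and the success criterion, and restate the power. For example: 35 evaluable, Bonferroni over 8, per-region power .52 at dz 0.5, 80% power for dz 0.64. Over 3 the figures are .67 and dz 0.57. If success means at least one region, say so and state how many regions are assumed active.

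For the 7T Monetary Incentive Delay version, naming one midbrain region as primary, tested at two-tailed .05, would make its .80 true in the same way.

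The cost is protocol wording, with no added enrolment. Under option 1 the other regions become secondary; under option 2 the stated power becomes less favourable.
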